13.8 Accrual Monitoring Stopping Rule

Given the expected accrual rate is around 1 patient per month, it is expected that the study will take around 36 months to fully accrue. We plan to monitor the accrual continually and if we only end up accruing 4 patients or less in the first year (after study activation), we will consider stopping the trial for slow accrual.

13.9 Primary Endpoint Completion Time Estimation (For clinicaltrials.gov reporting)

The primary endpoint is a comparison of PFS between the 2 treatment arms, as discussed in detail in [section 13.2](#). The final analysis is expected to take place around 5 years after the study begins, so we expect that the primary endpoint completion time to be around 5 years after study activation.

13.10 Descriptive Factors

- Metastatic Disease outside the chest: Yes vs. No
- Any prior chemo/TKI regimens: Yes vs. No
 - Prior VEGFR TKI: Yes or No
 - Prior targeted therapy other than VEGFR TKI: Yes or No
 - Prior cytotoxic chemotherapy (e.g., doxorubicin, paclitaxel): Yes or No
 - Prior RAI: Yes or No
 - Prior RAI > 600mCi: Yes or No
 - Prior Thyroidectomy: Yes or no
- Any lesion with SUVmax > 5 (from PET/CT scan in prior 6 months): Yes vs. No

13.11 Inclusion of Women and Minorities

This study will be available to all eligible patients, regardless of race, gender, or ethnic origin. There is no information currently available regarding differential effects of this regimen in subsets defined by race, gender, or ethnicity, and there is no reason to expect such differences to exist. Based on prior studies involving similar disease sites, we expect about 20% of patients will be classified as minorities by race and about 70% of patients to be women. Expected sizes of racial by gender subsets are shown in the following table:

Accrual Targets			
Ethnic Category	Sex/Gender		
	Females	Males	Total
Hispanic or Latino	1	1	2
Not Hispanic or Latino	23	9	32
Ethnic Category: Total of all subjects	24	10	34
Racial Category			
American Indian or Alaskan Native	1	1	2
Asian	2	1	3
Black or African American	2	1	3
Native Hawaiian or other Pacific Islander	1	1	2
White	18	6	24
Racial Category: Total of all subjects	24	10	34

Ethnic Categories: **Hispanic or Latino** – a person of Cuban, Mexican, Puerto Rican, South or Central American, or other Spanish culture or origin, regardless of race. The term “Spanish origin” can also be used in addition to “Hispanic or Latino.”

Not Hispanic or Latino

Racial Categories: **American Indian or Alaskan Native** – a person having origins in any of the original peoples of North, Central, or South America, and who maintains tribal affiliations or community attachment.

Asian – a person having origins in any of the original peoples of the Far East, Southeast Asia, or the Indian subcontinent including, for example, Cambodia, China, India, Japan, Korea, Malaysia, Pakistan, the Philippine Islands, Thailand, and Vietnam. (Note: Individuals from the Philippine Islands have been recorded as Pacific Islanders in previous data collection strategies.)

Black or African American – a person having origins in any of the black racial groups of Africa. Terms such as “Haitian” or “Negro” can be used in addition to “Black or African American.”

Native Hawaiian or other Pacific Islander – a person having origins in any of the original peoples of Hawaii, Guam, Samoa, or other Pacific Islands.

White – a person having origins in any of the original peoples of Europe, the Middle East, or North Africa.

14.0 CORRELATIVE AND COMPANION STUDIES

There are no correlative or companion studies available for A091302.

15.0 GENERAL REGULATORY CONSIDERATIONS AND CREDENTIALING

There are no credentialing requirements for A091302.

APPENDIX I REGISTRATION FATIGUE/UNISCALE ASSESSMENTS**Registration Fatigue/Uniscale Assessments**

Prior to patient registration, this form is to be administered by a nurse/CRA, completed by the patient, and recorded on the Registration Fatigue/Uniscale Assessments Form (see Forms Packet).

[figure not shown]
If needed, this appendix can be adapted to use as a source document. A booklet containing this assessment does not exist – please do not order this booklet.

How would you describe:

your level of fatigue, on the average in the past week including today?

your overall quality of life in the past week including today?

APPENDIX II ALLIANCE A091302 OPTIONAL MEDICATION CALENDARS**PATIENT MEDICATION DIARY – Sorafenib 28-day cycle**

Today's date _____

Agent: **Sorafenib**Patient Name _____ (*initials acceptable*) Patient Study ID _____**INSTRUCTIONS TO THE PATIENT:**

1. Complete one form for each 4 week-period while you take **sorafenib**.
2. **Sorafenib should be taken twice daily on an empty stomach one hour before or two hours after eating. These tablets should be swallowed whole and cannot be crushed or chewed.**
3. Record the date, the number of capsules you took, and when you took them. Record doses as soon as you take them; do not batch entries together at a later time.
4. If you have any comments or notice any side effects, please record them in the Comments column. If you make a mistake while you write, please cross it out with one line, put your initials next to it, and then write the corrected information next to your initials. Example: ~~10:30 am~~ SB 9:30 am
5. Please return this form to your physician when you go for your next appointment.

Day	Date	Time of daily doses(am/pm)	# of capsules taken	Comments
1				
2				
3				
4				
5				
6				
7				
8				
9				
10				
11				
12				
13				
14				
15				
16				
17				
18				
19				
20				
21				
22				
23				
24				

Day	Date	Time of daily doses (am/pm)		# of capsules taken	Comments
25					
26					
27					
28					

Physician's Office will complete this section:

1. Date patient started protocol treatment

2. Date patient was removed from study

3. Total number of capsules taken this month (each size)

4. Physician/Nurse/Data Manager's Signature

Patient's signature

PATIENT MEDICATION DIARY – Sorafenib 56-day cycle

Today's date _____

Agent: **Sorafenib**Patient Name _____ (*initials acceptable*) Patient Study ID _____

INSTRUCTIONS TO THE PATIENT:

1. Complete one form for each 8 week-period while you take **sorafenib**.
2. **Sorafenib should be taken twice daily on an empty stomach one hour before or two hours after eating. These tablets should be swallowed whole and cannot be crushed or chewed.**
3. Record the date, the number of capsules you took, and when you took them. Record doses as soon as you take them; do not batch entries together at a later time.
4. If you have any comments or notice any side effects, please record them in the Comments column. If you make a mistake while you write, please cross it out with one line, put your initials next to it, and then write the corrected information next to your initials. Example: ~~10:30 am~~ SB 9:30 am
5. Please return this form to your physician when you go for your next appointment.

Day	Date	Time of daily doses(am/pm)	# of capsules taken	Comments
1				
2				
3				
4				
5				
6				
7				
8				
9				
10				
11				
12				
13				
14				
15				
16				
17				
18				
19				
20				
21				
22				
23				
24				
25				
26				

Day	Date	Time of daily doses (am/pm)	# of capsules taken	Comments
27				
28				
29				
30				
31				
32				
33				
34				
35				
36				
37				
38				
39				
40				
41				
42				
43				
44				
45				
46				
47				
48				
49				
50				
51				
52				
53				
54				
55				
56				

Physician's Office will complete this section:

1. Date patient started protocol treatment

2. Date patient was removed from study

3. Total number of capsules taken this month (each size)

4. Physician/Nurse/Data Manager's Signature

Patient's signature

PATIENT MEDICATION DIARY – Everolimus 28-day cycle

Today's date _____ **Agent: Everolimus**
Patient Name _____ (*initials acceptable*) **Patient Study ID** _____

INSTRUCTIONS TO THE PATIENT:

1. Complete one form for each 4 week-period while you take everolimus.
2. **Everolimus should be administered once daily at approximately the same time each day with or without food. Tablets should be swallowed whole with a glass of water. The tablets must not be chewed or crushed and grapefruit juice or grapefruit should be avoided.**
3. Record the date, the number of capsules you took, and when you took them. Record doses as soon as you take them; do not batch entries together at a later time.
4. If you have any comments or notice any side effects, please record them in the Comments column. If you make a mistake while you write, please cross it out with one line, put your initials next to it, and then write the corrected information next to your initials. Example: ~~10:30 am~~ SB 9:30 am
5. Please return this form to your physician when you go for your next appointment.

Day	Date	Time of daily dose	# of tablets taken	Comments
1				
2				
3				
4				
5				
6				
7				
8				
9				
10				
11				
12				
13				
14				
15				
16				
17				
18				
19				
20				
21				
22				
23				
24				

Day	Date	Time of daily dose	# of tablets taken	Comments
25				
26				
27				
28				

Physician's Office will complete this section:

1. Date patient started protocol treatment

2. Date patient was removed from study

3. Total number of tablet's taken this month (each size)

4. Physician/Nurse/Data Manager's Signature

Patient's signature

PATIENT MEDICATION DIARY – Everolimus 56-day cycle

Today's date _____

Agent: EverolimusPatient Name _____ (*initials acceptable*) Patient Study ID _____**INSTRUCTIONS TO THE PATIENT:**

1. Complete one form for each 8 week-period while you take **everolimus**.
2. **Everolimus should be administered once daily at approximately the same time each day with or without food. Tablets should be swallowed whole with a glass of water. The tablets must not be chewed or crushed and grapefruit juice or grapefruit should be avoided.**
3. Record the date, the number of capsules you took, and when you took them. Record doses as soon as you take them; do not batch entries together at a later time.
4. If you have any comments or notice any side effects, please record them in the Comments column. If you make a mistake while you write, please cross it out with one line, put your initials next to it, and then write the corrected information next to your initials. Example: ~~10:30 am~~ SB 9:30 am
5. Please return this form to your physician when you go for your next appointment.

Day	Date	Time of daily dose	# of tablets taken	Comments
1				
2				
3				
4				
5				
6				
7				
8				
9				
10				
11				
12				
13				
14				
15				
16				
17				
18				
19				
20				
21				
22				
23				
24				
25				
26				

Day	Date	Time of daily dose	# of tablets taken	Comments
27				
28				
29				
30				
31				
32				
33				
34				
35				
36				
37				
38				
39				
40				
41				
42				
43				
44				
45				
46				
47				
48				
49				
50				
51				
52				
53				
54				
55				
56				

Office will complete this section:

1. Date patient started protocol treatment

2. Date patient was removed from study

3. Total number of tablet's taken this month (each size)

4. Physician/Nurse/Data Manager's Signature

Patient's signature

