8.2 Dose Modifications for Sorafenib

- If multiple adverse events are seen, administer dose based on greatest reduction required for any single adverse event observed. Reductions or increases apply to treatment given in the preceding cycle and are based on adverse events observed since the prior dose.
- Sorafenib will not be re-escalated once reduced
- If dose reductions beyond dose level -2 is required or sorafenib is held for 4 weeks, sorafenib will be discontinued.
- If more than one of these toxicities apply, use the most stringent criteria (i.e., the greatest dose reduction.)
- If the patient experiences a significant adverse event requiring a dose reduction at the start of the next cycle, then the dose will remain lowered.

CTEP-AERS reporting may be required for some adverse events (See [Section 9.0](#))

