8.2.1 Dose levels

Dose reduction of sorafenib will be performed according to the table below. Sorafenib will be permanently discontinued for patients who require dose interruptions of > 28 days or who experience dose limiting toxicities at dose level -2. Missed doses of sorafenib will not be made up.

Dose Level	Drug Name	Dose
0*	Sorafenib	400mg twice daily
-1	Sorafenib	200mg twice daily
-2	Sorafenib	200mg daily

*Dose level 0 refers to the starting dose.

- If dose reductions beyond the lowest dose level are required discontinue all protocol therapy.
- Doses that have been reduced will not be re-escalated.

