8.2.2 Dose Modifications for Hematologic Toxicities

Grade ≥ 3 neutropenia, thrombocytopenia, or neutropenic fever: Interrupt sorafenib until \leq grade 2, then resume with one dose level reduction of sorafenib for all subsequent doses.

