8.3 Dose Modifications for Sorafenib + Everolimus

- If multiple adverse events are seen, administer dose based on greatest reduction required for any single adverse event observed. Reductions or increases apply to treatment given in the preceding cycle and are based on adverse events observed since the prior dose.
- Sorafenib or everolimus will not be re-escalated once reduced
- If dose reductions beyond dose lowest dose level is required OR sorafenib or everolimus is held for 4 weeks, sorafenib or everolimus will be discontinued. If 1 agent is discontinued, the patient may remain on the other agent. If sorafenib is discontinued and everolimus has never been dose reduced, the patient may have everolimus dose increased to 10 mg daily. In this scenario, dose level chart for everolimus in [section 8.4.1](#) should be used.
- If more than one of these toxicities apply, use the most stringent criteria (i.e., the greatest dose reduction.).

CTEP-AERS reporting may be required for some adverse events (See [Section 9.0](#))

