8.3.1 Dose levels

Dose reduction of sorafenib and everolimus will be performed according to the table below. Sorafenib or everolimus will be permanently discontinued for patients who require dose interruptions of > 28 days or who experience dose limiting toxicities at dose level -2. Missed doses of sorafenib or everolimus will not be made up. To clarify, only the dose level of the offending agent needs to be dose reduced as per protocol if it is clear that the other drug did not cause the adverse event (e.g., only sorafenib needs to be dose reduced for hand-foot syndrome). If there are any questions, please discuss with protocol PI ([name]).

Dose Level	Drug Name	Dose	Drug Name	Dose
0*	Sorafenib	400 mg twice daily	Everolimus	5mg daily
-1	Sorafenib	200 mg twice daily	Everolimus	2.5mg daily
-2	Sorafenib	200mg daily	Everolimus	2.5mg every other day

*Dose level 0 refers to the starting dose.

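### All four optional patient diaries print a fixed dosing frequency that is wrong at dose level -2: sorafenib in both arms, everolimus in the combination arm

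*Combined protocol and SAP*

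**What the plan says.** Appendix II supplies four optional diaries: sorafenib and everolimus, each in a 28-day and a 56-day form. Item 2 of both sorafenib forms reads "Sorafenib should be taken twice daily on an empty stomach one hour before or two hours after eating". The same sentence is the footnote to the starting regimens in Section 7.0. Item 2 of both everolimus forms gives a once-daily schedule. No form states milligrams or tablets per dose, has a space for the prescribed schedule, or says that a dose reduction may change the frequency. Item 1 of the 28-day sorafenib form, "Complete one form for each 4 week-period while you take" sorafenib, makes no provision for a new sheet when the dose changes.

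The dose tables change the frequency as well as the amount. Sorafenib level -2 is 200 mg once a day for sorafenib alone (8.2.1) and in the combination (8.3.1). Everolimus level -2 in the combination is "2.5mg every other day" (8.3.1). For everolimus alone, level -2 is 2.5 mg once a day (8.4.1).

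Reductions are one-way: "Sorafenib will not be re-escalated once reduced" (8.2), "Doses that have been reduced will not be re-escalated" (8.2.1) and "Sorafenib or everolimus will not be re-escalated once reduced" (8.3).

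**The concern.** The diary is a sponsor-written sheet under a heading of patient instructions, and at level -2 its frequency contradicts the assigned schedule. Patients at level -2 have usually been reduced twice for toxicity. If one of them takes the tablet count from the site's instruction and the frequency from the diary, the dose returns to level -1, undoing a reduction that the protocol says is not to be reversed. What is at stake is avoidable over-dosing in patients who have already shown poor tolerance.

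Dose changes will be common enough for the tables to be used. Section 1.1 reports dose modification in 77% of sorafenib patients in the phase III trial, and Section 1.3 reports dose reduction in 75% of patients at the combination's maximum tolerated dose. Neither figure says how many patients would reach level -2 here.

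**Working it through.** **Inputs.** Diary frequencies: item 2 of each form, Appendix II. Dose levels: tables in 8.2.1, 8.3.1 and 8.4.1. Sorafenib tablet strength: 200 mg (10.1). Everolimus 2.5 mg tablets: available (10.2). Visit intervals: every 2 weeks in cycles 1-2, every 4 weeks in cycles 3-12, every 8 weeks from cycle 13 (5.0).

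**Frequency comparison.**

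| Drug and table | Level 0 | Level -1 | Level -2 | Diary | Conflict |
|---|---|---|---|---|---|
| Sorafenib, 8.2.1 and 8.3.1 | 400 mg twice daily | 200 mg twice daily | 200 mg daily | twice daily | level -2 only |
| Everolimus in combination, 8.3.1 | 5 mg daily | 2.5 mg daily | 2.5 mg every other day | once daily | level -2 only |
| Everolimus alone, 8.4.1 | 10 mg daily | 5 mg daily | 2.5 mg daily | once daily | none |

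The last row covers crossover patients. It also covers combination patients who stop sorafenib and are raised under 8.3: "If sorafenib is discontinued and everolimus has never been dose reduced, the patient may have everolimus dose increased to 10 mg daily". Those patients move to the 8.4.1 table and have no conflict.

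**Daily dose if the diary frequency is followed at level -2.**

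- Sorafenib: assigned 1 x 200 = 200 mg/day; by diary 2 x 200 = 400 mg/day, equal to level -1. Ratio 400/200 = 2.0; excess 200 mg/day (one tablet).
- Everolimus in combination: assigned 2.5/2 = 1.25 mg/day on average; by diary 2.5 mg/day, equal to level -1. Ratio 2.5/1.25 = 2.0; excess 1.25 mg/day (one 2.5 mg tablet every two days).

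**Worst case: one full visit interval with no correction.** Tablets taken versus assigned:

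| Interval | Sorafenib 200 mg | Excess | Everolimus 2.5 mg | Excess |
|---|---|---|---|---|
| 14 days (cycles 1-2) | 28 vs 14 | 14 x 200 = 2,800 mg | 14 vs 7 | 7 x 2.5 = 17.5 mg |
| 28 days (cycles 3-12) | 56 vs 28 | 28 x 200 = 5,600 mg | 28 vs 14 | 14 x 2.5 = 35 mg |
| 56 days (from cycle 13) | 112 vs 56 | 56 x 200 = 11,200 mg | 56 vs 28 | 28 x 2.5 = 70 mg |

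Visit windows of +/- 3 days (cycles 1-2) and +/- 7 days (later) shift these totals slightly.

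**Supply condition.** The totals assume the patient holds enough tablets. If the site dispenses exactly the level -2 quantity, a doubled dose exhausts it half-way: day 28/2 = 14 of a 28-day cycle, or day 56/2 = 28 of a 56-day cycle. Going further needs surplus tablets, for example left over from a higher level. Dispensing quantities are not in the documents.

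**Upper bound on patients.** Section 13.4 caps accrual at 34, 17 per arm. The everolimus conflict can therefore reach at most 17 planned patients, and the sorafenib conflict at most 34. In each case only patients at level -2 who use a diary are exposed.

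**The case against.** The strongest reply is that the diary cannot be the dosing instruction. It is optional and gives no tablet count, so every patient must get the dose elsewhere. Harm needs a patient to use that source for the count and ignore it for the frequency. Nothing in the documents suggests that sites dose this way. Labels are not in the documents and consent pages were removed, so the likelihood cannot be judged.

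There are also safeguards. Most reductions follow an interruption and a restart at a named level, as in 8.2.2 ("then resume with one dose level reduction of sorafenib for all subsequent doses"), which is a natural moment for a fresh instruction. The diary is returned at the next appointment and the office totals the tablets, so a doubled count would show. Limited supply could expose the error sooner. Finally, the rules against re-escalation govern what is assigned; a patient misreading a sheet makes an administration error and does not breach those rules.

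Most of this stands, and it is why the point is minor. The last remark is fair as far as it goes: the diary authorises nothing. The effect on the dose taken would still be the one those rules are meant to prevent. The returned diary detects the error only after the doses have been swallowed. Optional status narrows the reach but does not make the sheet correct for those who use it.

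**Conclusion.** The concern holds. All four diaries carry a frequency that is wrong at a permitted dose level, and no wording on the sheets resolves it. For a patient who followed the sheet at level -2, the dose would be exactly 2.0 times that assigned. The tablet totals are worst cases: they assume no correction before the next visit and enough tablets in hand. The number of patients who would reach level -2, use a diary and take the frequency from it is unknown and may be zero. Confidence is high in the mismatch; how often it would lead to over-dosing cannot be established from the documents. The point has no bearing on the endpoint, the analysis or the stopping rules. It should be corrected as a small safety matter because the correction is nearly free.

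**What to change.** In item 2 of each of the four diaries, replace the printed frequency with *as directed by your study team* and keep the guidance on food and swallowing. The cost is one phrase per form. The drawback is that patients at levels 0 and -1 lose the reminder of the usual frequency.

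The alternative keeps that reminder: add one line to each form for the site to enter tablets per dose and frequency at dispensing. If a new sheet is then issued when the dose changes, item 1 should allow it, for example *one form for each 4-week period, or from each dose change* (8-week on the 56-day forms).

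The dose levels in Section 8 and the footnotes in Section 7.0 need no change. The sheets' references to capsules could be changed to tablets at the same time, as an editorial matter only.
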